## **Safety Analyses**

The analysis population for the safety analyses will be the As-Treated population. Safety data will be described as follows.

- The sort order of listings will be the participant number within randomized treatment arm.
- Summary information will be grouped according to randomized treatment arm.
- Continuous data will be summarized using descriptive statistics (median, minimum, maximum, mean, standard deviation and number with non-missing data.)
- Categorical data that is not ordered will be summarized with frequencies, percents, and number with non-missing data.
- When calculating the incidence of adverse events, or any sub-classification thereof by treatment, time period, severity, etc., each participant will only be counted once and any repetitions will be ignored; the denominator will be the total population size.

Per ClinicalTrial.gov reporting requirements, three tables summarizing adverse events are required:

- All-Cause Mortality: A table of all anticipated and unanticipated deaths due to any cause, with number and frequency of such events in each arm/group of the trial.
- SAEs: A table of all anticipated and unanticipated serious adverse events, grouped by organ system, with number and frequency of such events in each arm of the trial.
- Other (Not Including Serious) AEs: A table of anticipated and unanticipated events (not included in the serious adverse event table) that exceed an incidence rate of 5% on either arm of the trial, grouped by organ system, with number of such events in each arm/ of the trial.

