## 10.4 STATISTICAL ANALYSIS

### 10.4.1 Analysis Populations

The intention to treat (ITT) population will include all participants randomized and will be used to assess primary, secondary and exploratory efficacy outcomes. The as-treated population will include all randomized participants who received at least one dose of study medication and will be used to assess safety outcomes. An additional secondary analysis dataset will be used to assess the robustness of the primary efficacy endpoint: The per protocol dataset is defined as the ITT population excluding patients who are noncompliant with study medication and who have major protocol deviations.

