#### **Secondary Endpoints**

Secondary outcome for this study will be assessed from baseline to the end of study for each patient. The following secondary outcomes will be analyzed using the ITT population:

1. Incidence of a decline from baseline in percent predicted FVC of 10% or greater during the study period.
2. Frequency of progressive disease as defined by Outcome Measures in Rheumatology (OMERACT): Relative decline from baseline in percent predicted FVC of  $\geq 10\%$ , or relative change from baseline in percent predicted FVC  $\geq 5\%$  and  $< 10\%$ , and  $\geq 15\%$  relative decline in diffusing capacity of lung for carbon monoxide (DLCO) (Khanna, Mittoo et al. 2015)
3. Change from baseline to end of study in absolute value of FVC
4. Change from baseline to end of study of percent predicted FVC
5. Slope of percent predicted FVC over 52-week treatment period
6. Slope of absolute value of FVC over study period
7. Time to decline of 10% or greater in percent predicted FVC or death while on study
8. Change from Baseline to end of study in dyspnea, as measured by the Dyspnea 12 questionnaire

The following secondary outcomes will be analyzed using the as-treated population:

9. Proportion of participants with all-cause mortality
10. Proportion of participants with all-cause hospitalization
11. Proportion of participants with hospitalization for respiratory cause
12. Number of acute exacerbations requiring hospitalizations
13. Proportion of participants with and number of treatment-emergent adverse events (AEs)
14. Proportion of participants with and number of treatment-emergent serious adverse events (SAEs)
15. Proportion of participants with and number of treatment-emergent/treatment-related AEs
16. Proportion of participants with and number of treatment-emergent/treatment-related SAEs
17. Proportion of participants with and number of AEs leading to early discontinuation of

study treatment

18. Proportion of participants with and number of treatment-emergent death or transplant

19. Proportion of participants with and number of treatment-emergent RA-ILD-related mortality

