### **Intention to Treat (ITT) population (full analysis set):**

Defined as all participants who were randomized. The ITT population will be used for all primary, secondary, and exploratory efficacy analyses.

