### **Safety population (as-treated population)**

Defined as all randomized participants who received any study medication and who received at least one study medication dose. The Safety population will be used for safety-related analyses.

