## **Protocol Deviations**

Important protocol deviations will be listed for all participant providing consent.

1. Those who entered the study even though they did not satisfy the entry criteria.
2. Those who developed withdrawal criteria during the study but were not withdrawn: Patients with visit dates out of visit window will be included in the ITT population and the per protocol population.
3. Randomized participants who report taking excluded medications will be included in the ITT population only.

Protocol deviations will be summarised by center and grouped into the following categories:

- Informed consent deviation
- Study procedure not completed (laboratory, serology, liver enzymes, ecg, biomarkers, patient reported outcome questionnaire, physician global assessment, hrct, diffusion capacity/lung volumes, physical exam, oxygen saturation)
- Study procedure performed incorrectly
- Eligibility violation (FVC  $\leq$ 40%, change in FVC  $>$ 10%, FEV1/FVC ratio  $<$ 0.7, spirometry quality not met, eGFR out of range)

- Study medication dose error/not taken as prescribed error
- Prohibited medication (Nintedanib)
- Visit or procedure performed out of window
- Missed visit
- Other (incorrect equipment, incorrect/missing drug diary, additional/duplicate procedure, procedure/visit done over multiple days, study medication dispensed at incorrect visit, wrong medication (clofazimine), extra blood drawn)

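### The SAP calls its safety set 'as-treated' but tabulates it by randomized arm, so anyone given the other arm's capsules would be counted under the drug not taken

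*SAP*

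**What the plan says.** The SAP section on Safety Analyses fixes the population first: "The analysis population for the safety analyses will be the As-Treated population". The rules that follow deal with layout. For listings: "The sort order of listings will be the participant number within randomized treatment arm". For tables: "Summary information will be grouped according to randomized treatment arm".

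The population is defined in two places, both times as an inclusion rule only. The SAP, under Safety population, has: "Defined as all randomized participants who received any study medication and who received at least one study medication dose". Protocol 10.4.1 has: "The as-treated population will include all randomized participants who received at least one dose of study medication". Neither says which product a participant is counted under.

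The later SAP sections on adverse events, serious adverse events and laboratory evaluations refer only to treatment arm or treatment group, so the Safety Analyses rule governs them. SAP Secondary Endpoints assigns items 9 to 19 (mortality, hospitalization, exacerbations, adverse events) to the same set: "The following secondary outcomes will be analyzed using the as-treated population".

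**The concern.** A reader of the final report who sees the label as-treated will assume that events sit under the drug taken. Under the SAP they sit under the drug assigned. The two differ only for a participant who received the other arm's product, but for that participant the SAP's rule puts reactions to pirfenidone in the placebo column, or placebo experience in the pirfenidone column. Either error pulls the arms together and so tends to hide drug-related harm.

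Such an error could pass unnoticed during the trial. The capsules look the same and the packs carry identical labels (Protocol 10.5.1). Supply is handed out at randomization and again at weeks 13, 26 and 39 (Protocol 7.2), and could be shipped to homes during the pandemic (Protocol 17.1). If a mix-up came to light only at unblinding, a grouping rule chosen then would be chosen with its effect in view.

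**Working it through.** **1. Grouping rules side by side.**

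| Analysis | Who is included | Grouped by |
|---|---|---|
| ITT efficacy (SAP, Efficacy Analyses) | all randomized | randomized arm |
| Safety (SAP, Safety Analyses; Protocol 10.4.1) | all randomized with at least one dose | randomized arm |
| As-treated in the usual sense | all with at least one dose | product received |

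The second row differs from the first only by removing undosed participants. No section supplies the rule in the third row.

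**2. The plan's own safety figure.** The documents attach no number to the grouping rule. The nearest figure is in Protocol 10.3: a 72% chance of seeing at least one event with a 1% rate among 127 participants on pirfenidone. The formula is 1 − (1 − p)^127. At p = 0.01 it gives 0.721, at 0.02 it gives 0.923 and at 0.035 it gives 0.989, against stated values of 0.72, 0.92 and 0.99. These reproduce, and the choice of grouping does not alter them.

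**3. Size of the dilution.** Inputs:

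- 123 participants randomized (SAP, Actual Sample Size). The arm split is not stated; 62 pirfenidone and 61 placebo is an assumption based on 1:1 allocation.
- Event rates for ALT/AST at or above three times the upper limit: 3.7% on pirfenidone, 0.8% on placebo (Protocol 6.1.9), used only as an example.
- Each wrongly supplied participant is assumed to have taken the other product throughout, which is the worst case for that person.

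Let k1 be the number randomized to pirfenidone but given placebo, and k2 the reverse. Under randomized-arm grouping the expected rates are

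- pirfenidone column: [(62 − k1) × 0.037 + k1 × 0.008] / 62
- placebo column: [(61 − k2) × 0.008 + k2 × 0.037] / 61

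Their difference equals 0.029 × (1 − k1/62 − k2/61).

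| k1 | k2 | Pirfenidone column | Placebo column | Difference (points) | Share of true difference |
|---|---|---|---|---|---|
| 0 | 0 | 3.70% | 0.80% | 2.90 | 100% |
| 1 | 0 | 3.65% | 0.80% | 2.85 | 98.4% |
| 0 | 1 | 3.70% | 0.85% | 2.85 | 98.4% |
| 1 | 1 | 3.65% | 0.85% | 2.81 | 96.7% |
| 2 | 2 | 3.61% | 0.90% | 2.71 | 93.5% |
| 3 | 3 | 3.56% | 0.94% | 2.62 | 90.2% |

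One case costs 1/62 or 1/61 of the difference, about 1.6%. Grouping by product received would keep the full 2.90 points in every row.

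**The case against.** The best defence is that the SAP does not contradict itself. As-treated is defined purely by dosing, one grouping rule is stated, and a programmer following it has no choice to make. The complaint would then concern a label and an event that nobody has recorded. Much of this stands: the clash is between a name and a rule, not between two rules, and nothing in the documents says that anyone received the wrong arm's product. What remains is that the one stated rule gives the wrong answer in the one situation where the label matters.

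Three stronger readings may tempt a reader. None is supported.

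- *That the deviation list shows wrong-arm supply.* It does not. The category "study medication dispensed at incorrect visit" is an error of timing, and the dose-error category concerns how the medication was taken. The only wrong medication named there is clofazimine, which is not a study product.
- *That mortality and hospitalization have been wrongly taken out of ITT.* The SAP says: "The ITT population will be used for all primary, secondary, and exploratory efficacy analyses". That sentence concerns efficacy. It is true that Protocol 4.2.2 heads its whole list as efficacy measures, but that list also contains adverse-event counts, so the heading cannot settle the matter. Protocol 10.4.3 restricts safety analyses to the as-treated population and gives hospitalization, transplant and death as examples. The Protocol Summary and the SAP preface also place hospitalization and all-cause mortality under safety. Death is in any case analysed in ITT, as a component of the primary endpoint (SAP, Efficacy Analyses).
- *That one misplaced participant could overturn a safety finding.* Moving one event from 4 v 0 to 3 v 1 (62 v 61) does take an uncorrected chi-square p-value from 0.044 to 0.317. But this supposes that the one misdosed person is also one of the four with the event. Under Fisher's exact test, which Protocol 10.4.3 also allows, 4 v 0 already gives 0.119. Secondary results are declared exploratory, so crossing 0.05 decides nothing.

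**Conclusion.** The point holds, as a conditional one. The safety set is ITT restricted to dosed participants under an as-treated name, and its grouping rule would count a wrongly supplied participant's events and laboratory values under the drug not taken. The direction of the error is predictable: towards no difference when the drug causes the event.

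The size is zero if no participant took the other arm's capsules, and the documents give no sign that anyone did. Otherwise it is about 1.6% of the expected difference per wrongly supplied participant, rising to roughly 10% with three in each arm. These figures rest on the assumed 62/61 split and on full-period exposure to the wrong product. The percentage loss does not depend on the event rates; the loss in percentage points does. Nothing here affects the primary efficacy analysis or any design figure. This is an inexpensive safeguard to settle in advance, not a defect that threatens the trial's conclusions.

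**What to change.** In SAP, Safety Analyses, replace randomized arm with treatment actually received as the basis for grouping summaries and sorting listings, and have the adverse-event and laboratory sections refer to it. Before unblinding, add a rule for participants who took both products. Report how many participants' received and randomized treatments differ, giving the number even if it is zero, and list each one with dates of exposure and events. Leave mortality and hospitalization in the as-treated set, as Protocol 10.4.3 has them.

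The cost is a few sentences and a comparison of dispensing records with the randomization list. The accountability log in Protocol 6.2 should supply the dispensing side; bottle returns are less useful, because the SAP notes that many bottles did not come back. There is one small downside. Any mixed-exposure rule will attribute some events to a product not being taken at the time; for example, counting a participant under pirfenidone after a single wrong bottle would charge mainly placebo-period events to the drug. Individual listings let the reader see this.

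If the team prefers randomized-arm grouping, it should at least drop the as-treated name. That corrects the label but not the misattribution.

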## **Adverse Events**

An AE is any untoward medical event associated with the use of a drug in humans, whether or not it is considered related to a drug. Adverse events will be coded from the actual term described by the investigator using the Medical Dictionary for Regulatory Activities (MedDRA).

Treatment-emergent AEs are events that first occur or increase in severity after the first study drug dose. In case of repeated events in participants, the proportions on each treatment arm will use the number of participants as the denominator, and the number of participants with at least one event as the numerator, so each participants will be counted once. Incidence of AEs by treatment arm will

be compared using chi square tests.

AEs will be summarized by treatment arm, overall and by system organ class, severity, and relationship to study drug.

The following body systems will be summarized according to treatment arm:

- Any Treatment-Emergent AEs
- Blood and Lymphatic System Disorders
- Cardiac Disorders
- Ear and Labyrinth Disorders
- Eye Disorders
- Gastrointestinal Disorders
- General Disorders
- Hepatobiliary Disorders
- Immune System Disorders
- Infections and Infestations
- Injury, Poisoning and Procedural Complications
- Metabolism and Nutrition Disorders
- Musculoskeletal and Connective Tissue Disorders
- Nervous System Disorders
- Psychiatric Disorders
- Renal and Urinary Disorders
- Reproductive System and Breast Disorders
- Respiratory, Thoracic and Mediastinal Disorders
- Skin and Subcutaneous Tissue Disorders
- Surgical and Medical Procedures

AE listings will be sorted by treatment arm, then participant ID, and will include the following:

- Treatment Emergent (yes/no)
- AE # for the participant
- AE Primary Category
- AE Event Term
- AE Start Date
- AE Stop Date
- Days from Start of Study Medication
- Severity Grade
- Expected?
- Relationship to Study Drug
- Study Drug Action Taken
- Outcome

### **Deaths, Serious AEs and other Significant AEs**

Separate summaries will be provided for deaths, serious AEs, and other AEs by treatment arm. Tables will include the number and percent. Summaries will be shown for the number of events and the number of patients experiencing the event. Frequency of SAEs by treatment arm will be compared using chi square tests.

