**PROTOCOL SUMMARY**

Title:
	
A Randomized, Double-Blind, Placebo-Controlled, Phase 2 Study of Safety, Tolerability and Efficacy of Pirfenidone in Patients with Rheumatoid Arthritis Interstitial Lung Disease

Précis:
	
A Phase 2, randomized, double blind, placebo controlled clinical trial designed to evaluate the efficacy and safety of administering pirfenidone or placebo for 52 weeks to subjects with RA-ILD. Patients meeting the eligibility criteria for the study will be randomized to receive either pirfenidone 2403 mg/d or placebo. Efficacy will be evaluated through interval testing of pulmonary function tests, patient reported outcomes, adverse events and survival. Safety will be assessed by determining differences between the treatment arms for the rate of adverse events, serious adverse events, rates of acute exacerbation, hospitalization and all-cause mortality.

Objectives:
	
To assess the efficacy and safety of pirfenidone 2403 mg/day as compared to placebo in patients with RA-associated interstitial lung disease.
 
To explore the role of peripheral blood biomarkers in predicting disease progression and survival in patients with RA-associated interstitial lung disease.
 
To explore a spectrum of validated questionnaires to assess disease specific PROs including overall health, and perspectives on symptoms, performance and quality of life.

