### 2.1.3.6 InterMune Pooled Phase 3 Safety Data

Safety results from the pooled PIPF-004 and PIPF-006 pirfenidone 2403 mg/d study population were similar to those in previous studies. Common treatment-emergent adverse events (AE) that occurred more frequently in the pirfenidone group than the placebo group included gastrointestinal disorders (nausea, diarrhea, dyspepsia, vomiting, and stomach discomfort), skin disorders (rash and photosensitivity reaction), anorexia, decreased appetite, fatigue, and dizziness. Although more pirfenidone 2403 mg/d than placebo patients had at least 1 dose reduction for at least 1 day, dose reductions implemented in accordance with the protocol-specified guidelines tended to be short-lived and were typically related to transient gastrointestinal events or skin disorders. The rate of treatment discontinuation due to an AE in the pirfenidone 2403 mg/d group was only 6% higher than in the placebo group. Mild or moderate serum transaminase elevations (serum ALT or AST  $>3 \times$  upper limit of normal [ULN]) occurred more frequently in patients treated with pirfenidone 2403 mg/d than placebo, but they were most often effectively managed with dose modification and not associated with untoward clinical consequences. More extreme elevations in serum ALT or AST ( $>10 \times$  ULN) were rare in both treatment groups, and no instances of liver function abnormality meeting the criteria for Hy's law occurred.

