**10.3 ADVERSE EVENTS**

Table 2A shows the probability of observing at least one adverse event among participants randomized to Pirfenidone under a range of assumptions for the background adverse event rate. The proposed sample size of 127 participants randomized to Pirfenidone will provide a 72% probability of observing an adverse event with a 1% background rate and a 99% probability of observing an adverse event that has a 3.5% background rate. Furthermore, with a goal of estimating an adverse event rate for this population with sufficient precision based on the proposed sample size, Table 2B shows that the two-sided 95%

confidence interval around the observed proportion will be sufficiently narrow for a range of adverse event rates.

**Table 2A:** Probability of observing at least one adverse event in the pirfenidone group (N=127), under a range of background adverse event rates.

Background Adverse Event Rate	Probability of Observing at Least One Adverse Event
0.010	0.72
0.020	0.92
0.035	0.99
0.050	1.00
0.100	1.00
0.150	1.00
0.200	1.00

**Table 2B:** Two-sided 95% confidence interval width for a range of observed adverse event proportions with 127 participants on Pirfenidone with complete data.

Observed Proportion	Confidence Interval Width	Lower Limit	Upper Limit
0.025	0.064	0.006	0.069
0.050	0.084	0.019	0.104
0.075	0.100	0.036	0.135
0.100	0.112	0.054	0.166
0.125	0.122	0.073	0.195
0.150	0.131	0.093	0.224
0.175	0.139	0.113	0.252
0.200	0.146	0.134	0.280

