## **Actual Sample Size**

Enrolment at centers was interrupted by the COVID-19 pandemic during March, 2020. After all centers were shut down for approximately three months, and after an interim DSMB meeting that focussed on the interruption of recruitment, a decision was made to permanently close enrolment. The final sample size is 123 randomized participants. The last participant was randomized on March 24, 2020.

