## **Subject Disposition**

Please refer to the accompanying spreadsheet for forms and variable names (TRAIL1 endpoints and dataset variable names.xlsx, Subject Disposition tab.)

The consort diagram will be presented.

<http://www.consort-statement.org/consort-statement/flow-diagram>

The number of participants reaching the milestones in the trial will show the number screened, randomized, and reaching each visit, or study close, and the number dropped out and for what reasons (death, toxicity, treatment failure, withdrew consent). A crosstabulation will show the accrual by quarter and by network and center. A listing of participant discontinuation from study medication will be presented for all randomized participants. Frequency counts and percentages of all participants providing informed consent, randomized/enrolled, completing and discontinuing from the study and study treatment will be presented according to treatment arm and overall. A summary of discontinuations will also be presented by visit. The proportion who discontinued the study early will be compared using chi-square test in the ITT population. The proportion who stopped treatment early on each arm will be compared using chi-square test in the as-treated population.

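### The SAP compares adverse events, serious adverse events and early treatment stopping by chi-square test without an effect estimate or confidence interval, although the protocol plans odds ratios with 95% intervals for its listed binary outcomes

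*SAP*

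**What the plan says.** The Protocol Summary sets the aim: "Safety will be assessed by determining differences between the treatment arms for the rate of adverse events, serious adverse events", together with acute exacerbation, hospitalization and death.

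The SAP then names the comparisons:

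- **Adverse events** (SAP, Adverse Events): "Incidence of AEs by treatment arm will" be compared by chi-square test.
- **Serious adverse events** (SAP, Deaths, Serious AEs and other Significant AEs): "Frequency of SAEs by treatment arm will be compared using chi square tests". The accompanying display is described as "Tables will include the number and percent".
- **Early stopping** (SAP, Subject Disposition): "The proportion who stopped treatment early on each arm will be compared using chi-square test in the as-treated population".

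None of these sections names a between-arm difference, ratio or interval. Elsewhere the SAP plans 95% intervals for the primary endpoint and its components, the longitudinal and time-to-event endpoints, and the exploratory subgroups.

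The protocol goes further in three places:

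- Section 10.4.2 reports unadjusted and adjusted odds ratios with 95% intervals, and extends similar analyses to the secondary binary outcomes of Section 4.2.2. Items 12 to 16 of that list cover adverse events, serious adverse events, the treatment-related subsets of both, and events leading to discontinuation.
- Section 10.2.2 says that observed effect sizes from the secondary outcomes are meant to inform later confirmatory trials.
- Section 10.4.3 allows chi-square or Fisher's exact test and plans time-to-event analysis of treatment-related discontinuation.

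The SAP says that it is based on protocol Section 10. On size it reports: "The final sample size is 123 randomized participants".

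**The concern.** Safety is half of the first study objective. A chi-square p-value does not give the size of a difference, or the excess risk that the data leave open. With less than half of the planned 270 participants, most true differences of moderate size will give p above 0.05, and a table of percents with such p-values can easily be read as reassurance. The protocol's stated use for these outcomes, effect sizes for later trials, needs estimates with their uncertainty. The SAP's safety sections do not carry over the estimates that the protocol appears to plan.

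**Working it through.** **Inputs.** 123 randomized (SAP, Actual Sample Size) and equal allocation (SAP, General Study Design and Plan). Assumed: 62 placebo and 61 pirfenidone, all dosed, and a two-sided 5% level. The SAP states that level for efficacy tests but gives none for the safety tests. The event rates below are mine, because the documents give no expected rate or excess for serious adverse events.

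**Step 1: reproduce the plan's own figure.** Protocol Table 1A gives 127 per arm for 85% power at 0.32 against 0.16. With pooled variance under the null and no continuity correction:

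n = [1.960 × √(2 × 0.24 × 0.76) + 1.036 × √(0.32 × 0.68 + 0.16 × 0.84)]² / 0.16²
= (1.184 + 0.615)² / 0.0256 ≈ 126.4, so 127.

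The protocol's figure reproduces with the uncorrected two-proportion test, which is the Pearson chi-square test.

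**Step 2: how often that test misses a true difference at 62 against 61.** Power is the sum, over all pairs of event counts, of the product of the two binomial probabilities wherever the Pearson statistic exceeds 3.8415.

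| Placebo | Pirfenidone | Power | Missed |
|---|---|---|---|
| 10% | 20% | 0.355 | 64% |
| 15% | 25% | 0.290 | 71% |
| 20% | 30% | 0.255 | 74% |
| 10% | 25% | 0.612 | 39% |

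Hand check of the first row by normal approximation, 61.5 per arm: (0.10 - 1.96 × √(2 × 0.15 × 0.85/61.5)) / √((0.09 + 0.16)/61.5) = (0.100 - 0.126)/0.0638 = -0.41, which gives power of about 0.34.

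Power reaches 80% only at about 29.5% against 10%, or 43% against 20%. At the planned 127 per arm, 10% against 20% would still be missed in 39% of trials (power 0.610).

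**Step 3: what the p-value leaves out.** Take 12/61 (19.7%) on pirfenidone and 6/62 (9.7%) on placebo, a difference of 0.0999.

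- *Test.* Pooled rate 18/123 = 0.1463. X² = 0.0999² / [0.1463 × 0.8537 × (1/61 + 1/62)] = 2.46, p = 0.12.
- *Risk difference.* Wilson limits are 0.1163 to 0.3131 for 12/61 and 0.0451 to 0.1955 for 6/62. Newcombe's interval combines them. Lower: 0.0999 - √(0.0804² + 0.0987²) = -0.027. Upper: 0.0999 + √(0.1164² + 0.0517²) = 0.227.
- *Variant.* The Miettinen-Nurminen upper limit is slightly higher. At a difference of 0.231 the constrained rates are 0.298 and 0.067, the variance is (0.298 × 0.702/61 + 0.067 × 0.933/62) × 123/122 = 0.00447, and (0.0999 - 0.231)/√0.00447 = -1.96. Its lower limit is again -0.027. Score-type intervals therefore run from -2.7 points to between 22.7 and 23.1 points, or about -3 to +23.
- *Odds ratio, unadjusted.* (12 × 56)/(49 × 6) = 2.29. The standard error of its logarithm is √(1/12 + 1/49 + 1/6 + 1/56) = 0.537, and the 95% interval is exp(0.827 ± 1.052), or 0.80 to 6.5.

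The result is not significant, yet the data are compatible with a small reduction and with an excess of about 23 points.

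**The case against.** The best defence is that the estimates are already available. Protocol 10.4.2 plans odds ratios with intervals for the listed binary outcomes, the SAP rests on protocol Section 10, and death is covered as a component of the primary endpoint. Part of this stands: it makes the point a gap between two documents. It does not close the gap, because the SAP sections governing these comparisons name only the test. Section 10.4.2 is also headed as efficacy, and Section 4.2.2 introduces its list as efficacy measures, so a programmer could fairly read safety outcomes as excluded.

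It is also true that low power comes from the sample size. An interval adds no power; it shows the uncertainty.

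A reader might infer four stronger points, which the documents do not support:

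- *That the p-value is the only comparison available.* Counts and percents by arm are tabulated, so a reader could derive a difference and an interval.
- *That the SAP treats p above 0.05 as proof of safety.* No sentence says so.
- *That harms quantified in the protocol would be missed by these tests.* Section 6.1.9 gives transaminase rates, but SAP Clinical Laboratory Evaluations uses shift tables and counts and names no chi-square test. Section 2.1.3.6 says "The rate of treatment discontinuation due to an AE in the pirfenidone 2403 mg/d group was only 6% higher than in the placebo group", but this has no base rate and concerns stopping because of an adverse event, while the SAP test covers stopping for any reason.
- *That protocol Table 2B commits the trial to these intervals.* Section 10.3 was written "with a goal of estimating an adverse event rate for this population with sufficient precision based on the proposed sample size", and its intervals describe the pirfenidone arm alone. A between-arm difference would not supply them.

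**Conclusion.** The point holds as a reporting gap with a simple remedy. For adverse events, serious adverse events and early stopping, the SAP names a test and no estimate, while the protocol plans odds ratios with 95% intervals for its listed binary outcomes and values effect sizes. At 123 participants a non-significant result says little: a doubling from 10% to 20% is missed in 64% of trials, and an observed 10-point excess can leave up to about 23 points not excluded. These figures rest on a 62/61 split, all participants dosed, a two-sided 5% level and rates that I chose for illustration. The primary analysis and its error rate are unaffected. The change should be made, but the plan's main conclusion does not depend on it.

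**What to change.** In SAP Subject Disposition, Adverse Events, and Deaths, Serious AEs and other Significant AEs:

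1. Report the risk difference, pirfenidone minus placebo, with a two-sided 95% score interval (name the variant, for example Miettinen-Nurminen). Apply it to participants with any treatment-emergent adverse event, any serious adverse event, any treatment-related adverse event or serious adverse event, any adverse event leading to discontinuation, and hospitalization, and to early treatment stopping.
2. Give the protocol 10.4.2 odds ratio and 95% interval alongside, or state that the risk difference replaces it for safety outcomes and why. Say whether the time-to-event analysis of treatment-related discontinuation in protocol 10.4.3 still stands.
3. Keep the p-value as descriptive, with Fisher's exact test when expected counts are small, as protocol 10.4.3 allows. State the threshold in advance.
4. Add one sentence: a non-significant difference will not be described as evidence of similar safety.

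The cost is a few lines before database lock and one extra column in the safety tables, with no new data. The drawback is that the intervals will be wide and the safety statement will look less reassuring.
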